4.2 Criteria for Removal from Study

Patients may voluntarily withdraw from the study (no further study data to be collected) at any time.

Patient death will be considered as a withdrawal from the study. Patients may also be withdrawn (the physician may decide to remove the patient from any further study activity) if any of the following occur:

1. Adverse event(s) (see section 7)
2. Disease progression
3. Major protocol deviation
4. Technical problems
5. Physician decision
6. Non-compliance with study treatment.
7. Death
8. Completed

Patients must be withdrawn if any of the following occur:

1. Lost to follow-up
2. Subject/guardian decision
3. Pregnancy (Pregnancy will be followed for outcome)

Patients lost to follow up should be recorded as such in the clinical trial record. For patients who are lost to follow-up, the investigator will record the attempts at “due diligence” by documenting in the source documents steps taken to contact the patient, e.g. dates of telephone calls, registered letters, etc.

4.3 Alternatives

The study agent is FDA approved and therefore has a well established safety and toxicity profile. The treatment options available to this study population are not existent. Therefore, minimal risk to the patient is expected. In the event that a patient is deemed to be at risk sufficiently great to preclude further study participation as outlined in this study protocol they may removed from the study.

5. INVESTIGATIONAL AGENT/DEVICE/PROCEDURE INFORMATION

5.1 Investigational Agent/Device/Procedure

Abemaciclib is FDA approved and in regular use for clinical practice. For further details please refer to the abemaciclib investigator brochure.

For clinicaltrials.gov and Stanford Clinical Trials Directory compliance

Intervention Description

1. Abemaciclib 200 mg orally twice daily
2. Number of Cycles: until progression or unacceptable toxicity develops.

Arms/Groups

1. single arm study

5.2 Availability

The drug will be provided by the manufacturer Lilly, pharmaceutical company.

5.3 Agent Ordering

The Stanford University designated Investigational Drug Services (IDS) pharmacy will handle agent ordering and compounding at their SOP level.

5.4 Agent Accountability

5.4.1 Study drug preparation and dispensation

The investigator and delegates, as well as other study personnel will instruct the patient to take abemaciclib according to protocol. Abemaciclib will be dispensed by authorized site personnel, and all doses recorded in the clinical trial record.

Abemaciclib received from the manufacturer will be stored in our investigational pharmacy and dispensed at the beginning of each cycle. This will only be after confirmation from the investigator or co-investigator that the patient is to continue and has received instructions on how to take the medicine per protocol.

5.4.2 Study drug packaging and labeling

The manufacturer will provide abemaciclib in clearly labeled packaging. Immediately before dispensing the medicine to the patient, the patient's Drug Label Form will be updated to link the medication to the patient.

5.4.3 Drug supply and storage

Abemaciclib will be stored according to the instructions specified on the drug labels and in the Investigator's Brochure. The drug supply will be in a secure location that only the investigator and authorized personnel may have access to.

5.5 Study drug compliance and accountability

5.5.1 Study drug compliance

The patient will be asked to keep a diary of taking the medication, as well as bringing pill bottles to each clinic visit. At each visit, the patient's compliance in study medication according to protocol will be assessed by the investigator and/or study personnel. This information will be entered into the Drug Accountability Form and captured into the source document at each visit, in their medication diary.

5.5.2 Study drug accountability

The IDS will maintain an accurate record of the shipment and dispensation of study drug in the drug accountability log. This will be made available to the appropriate regulatory authority upon request.

During therapy, the patient will be asked to regularly return all unused drug and packaging. All unused medication and packaging will be destroyed. At the completion of the therapeutic portion of the protocol, all stored medication and packaging will be destroyed.

6. DOSE MODIFICATIONS

Dose escalation guidelines

No doses escalation will be permitted on this study.

Dose modifications

For patients who do not tolerate the protocol-specified dosing schedule, dose adjustments are permitted in order to allow the patients to continue the abemaciclib treatment. Any changes in drug administration will be recorded in the clinical trial record.

For patients who do not tolerate the protocol-specified dosing schedule, adjustments are recommended in order to allow the patient to continue the study treatment. Refer to Section 7.3.1 for dose level reductions. For purposes of EDC entry, dose modification is defined as dose reductions and dose holds.

General guidelines for dose modifications

- For grade 1 and tolerable grade 2 treatment-related toxicities, with the exception of pneumonitis, patients may continue at the current dose of abemaciclib.
- For intolerable grade 2 treatment-related toxicities, with the exception of pneumonitis, dosing should be interrupted until resolution to grade 1 or lower followed by dose reduction to the next dose level.
- For grade 3 or grade 4 treatment-related toxicity, that is not considered by the investigator to be life-threatening, dosing should be interrupted and the patients should be followed until the toxicity resolution to grade 1 or lower. Following recovery from grade 3 or grade 4 events, study treatment may continue following a dose reduction to the next dose level, if, in the opinion of the Investigator, the patient continues to experience clinical benefit. For any grade 3 or grade 4 treatment-related toxicity that is considered by the investigator to be life-threatening, permanently discontinue study treatment.

All dose modifications, interruptions or discontinuations must be based on the worst preceding toxicity as graded by the NCI Clinical Toxicity Criteria version 5

Patients whose treatment is interrupted or permanently discontinued due to an AE must be followed until resolution or stabilization of the event. Patients requiring interruptions greater than 2 cycle (56 days) should be discontinued from abemaciclib treatment. All patients will be followed for safety until 30 days after the last dose of abemaciclib.

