7.3 Guidelines for on-study patient management

7.3.1 Guidelines for Diarrhea Management

Clinical trial data indicates the majority of patients who receive abemaciclib will develop diarrhea. Our experience indicates early identification and intervention for the management of diarrhea has been helpful to patients.

At enrollment, patients should receive instructions on the prompt management of diarrhea. In the event of diarrhea, supportive care measures should be initiated as early as possible. These include the following:

- At the first sign of loose stools, the patient should initiate antidiarrheal therapy (e.g. loperamide) and notify the investigator for further instructions and appropriate follow-up.
- Patients should also be encouraged to drink fluids (e.g., 8 to 10 glasses of clear liquids per day).
- Site personnel should assess response within 24 hours.
- Refer to Table 7-1 for additional information for diarrhea management and dose modification.

Table 7-1: Dose Modification and Management- Diarrhea

At the first sign of loose stools, start treatment with antidiarrheal agents, such as loperamide.

CTCAE Grade	Abemaciclib Dose Modifications
Grade 1	No dose modification is required.
Grade 2	If toxicity does not resolve within 24 hours to \leq Grade 1, suspend dose until resolution. Dose reduction is not required.
Grade 2 that persists or recurs after resuming the same dose despite maximal supportive measures	Suspend dose until toxicity resolves to \leq Grade 1. Resume at next lower dose.
Grade 3 or 4 or requires hospitalization	

Dose level reductions should be made in 50 mg increments. For example, if the starting dose of abemaciclib is 200 mg twice daily, dose reduction 1 would be 150 mg twice daily, dose reduction 2 would be 100 mg twice daily.

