7.3.4 General Guidance for Hepatic Monitoring

Alanine aminotransferase (ALT) and aspartate aminotransferase (AST) elevation are considered as ADR with the use of abemaciclib. **The following information in Table 7-3 is to be followed for hepatic monitoring:**

Table 7-3: Dose Modification and Management — Increased ALT/AST

Monitor ALT/AST prior to the start of abemaciclib therapy, every 2 weeks for the first 2 months, monthly for the next 2 months, and as clinically indicated.	
CTCAE Grade	Abemaciclib Dose Modifications
Grade 1 ($>\text{ULN}-3.0 \times \text{ULN}$) Grade 2 ($>3.0-5.0 \times \text{ULN}$)	No dose modification is required.
Persistent or Recurrent Grade 2, or Grade 3 ($>5.0-20.0 \times \text{ULN}$) that does not resolve with maximal supportive measures within 7 days to baseline or Grade 1	Suspend dose until toxicity resolves to baseline or Grade 1. Resume at next lower dose.
$\geq\text{Grade 2} (>3.0 \times \text{ULN})$ with total bilirubin $>2 \times \text{ULN}$, in the absence of cholestasis	Discontinue abemaciclib.
Grade 4 ($>20.0 \times \text{ULN}$)	Discontinue abemaciclib.

To ensure patient safety the investigator should collect specific recommended clinical information and follow-up laboratory tests as shown below in Table 7-4.

Details for hepatic monitoring depend upon the severity and persistence of observed laboratory test abnormalities. If a study patient experiences elevated ALT/AST 5×ULN and elevated TBL 2×ULN, or ALT/AST 8×ULN, liver tests, including ALT, AST, TBL, direct bilirubin, gamma-glutamyl transferase (GGT), and creatine phosphokinase (CPK), should be repeated within 3 to 5 days to confirm the abnormality and to determine if it is increasing or decreasing. If the abnormality persists or worsens, clinical and laboratory monitoring should be initiated by the investigator, based on the hepatic monitoring tests below.

Table 7-4: Hepatic Monitoring Tests for a Hepatic Treatment Emergent Abnormality.

Hematology	Clinical Chemistry
Hemoglobin	Total bilirubin
Hematocrit	Direct bilirubin
Erythrocytes (RBCs - red blood cells)	Alkaline phosphatase (ALP)
Leukocytes (WBCs - white blood cells)	Alanine aminotransferase (ALT)
Differential:	Aspartate aminotransferase (AST)
Neutrophils, segmented	Gamma-glutamyl transferase (GGT)
Lymphocytes	Creatine kinase (CK)
Monocytes	
Basophils	
Eosinophils	
Platelets	
Cell morphology (RBC and WBC)	
Coagulation	Other Chemistry
Prothrombin time, INR (PT-INR)	Acetaminophen

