7.3.5 General Guidance for Hematology Toxicity and Dose Modification

Hematologic toxicities including neutropenia, leukopenia, anemia, and thrombocytopenia have been observed in patients treated with abemaciclib, and causality has been established. Severe (Grade 3 and 4) neutropenia was observed in patients receiving abemaciclib. Patients should be monitored closely for signs of infection, anemia, and bleeding. **The following instructions from Table 7-5 must be used to manage hematologic toxicities.**

Table 7-5: Dose Modification and Management — Hematologic Toxicities

Monitor complete blood counts prior to the start of abemaciclib therapy, every 2 weeks for the first 2 months, monthly for the next 2 months, and as clinically indicated.	
CTCAE Grade	Abemaciclib Dose Modifications
Grade 1 or 2	No dose modification is required.
Grade 3	Suspend dose until toxicity resolves to \leq Grade 2. Dose reduction is not required.
Grade 3, recurrent, or Grade 4	Suspend dose until toxicity resolves to \leq Grade 2. Resume at next lower dose.
Patient requires administration of a blood cell growth factor	Suspend abemaciclib dose for at least 48 hours after the last dose of blood cell growth factor and until toxicity resolves to \leq Grade 2. Resume abemaciclib at next lower dose unless the dose was already reduced for the toxicity that led to the use of the growth factor.

7.3.6 General Guidance for Nonhematologic Toxicities (excluding diarrhea, increased ALT and ILD/Pneumonitis) Monitoring

Nonhematologic toxicities excluding diarrhea

- Grade 1 or 2: No dose modification is required.
- Persistent or recurrent Grade 2 toxicity that does not resolve with maximal supportive measures within 7 days to baseline or Grade 1: suspend dose until toxicity resolves to baseline or Grade 1. Resume at next lower dose.
- Grade 3 or 4: suspend dose until toxicity resolves to baseline or Grade 1. Resume at next lower dose.

Table 7-6: Dose Modification and Management — Nonhematologic Toxicities Excluding Diarrhea, ALT/AST Increased, and ILD/Pneumonitis

CTCAE Grade	Abemaciclib Dose Modifications
Grade 1 or 2	No dose modification is required.
Persistent or recurrent Grade 2 toxicity that does not resolve with maximal supportive measures within 7 days to baseline or Grade 1	Suspend dose until toxicity resolves to baseline or Grade 1. Resume at next lower dose.
Grade 3 or 4	

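### For Grade 2 diarrhea, Section 6 and Table 7-1 use different criteria and lead to different actions with no stated precedence; Section 6 and Table 7-6 differ likewise for other nonhematologic Grade 2 events

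*Combined protocol and SAP*

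**What the plan says.** Section 6, under its general guidelines, has two bullets on Grade 2 toxicity. The first reads: "For grade 1 and tolerable grade 2 treatment-related toxicities, with the exception of pneumonitis, patients may continue at the current dose of abemaciclib". The second covers intolerable Grade 2 events, again excepting pneumonitis: "dosing should be interrupted until resolution to grade 1 or lower followed by dose reduction to the next dose level". The word *tolerable* is not defined.

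Table 7-1 in Section 7.3.1 does not mention tolerability. For Grade 2 diarrhea that has not come down to Grade 1 or lower within 24 hours, it says "suspend dose until resolution. Dose reduction is not required". For "Grade 2 that persists or recurs after resuming the same dose despite maximal supportive measures", the dose is suspended and then "Resume at next lower dose". The text above the table introduces it this way: "Refer to Table 7-1 for additional information for diarrhea management and dose modification".

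Section 7.3.6 and Table 7-6 cover nonhematologic toxicity other than diarrhea, ALT/AST increases and pneumonitis. Grade 2 needs no modification at first. The dose is suspended and then reduced for "Persistent or recurrent Grade 2 toxicity that does not resolve with maximal supportive measures within 7 days to baseline or Grade 1".

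Section 6 points to Section 7.3.1 only for the size of the dose steps, which are 50 mg: 200, then 150, then 100 mg twice daily.

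**The concern.** The two texts sort the same events on different axes, and neither defers to the other. A site that follows Section 6 and a site that follows Table 7-1 can treat the same episode of diarrhea differently, and each can believe it is compliant. Section 7.3.1 states that the majority of patients given abemaciclib develop diarrhea, so this is not a rare decision. The protocol also provides for participating sub-sites (Sections 7.4 and 11).

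The stakes run in both directions. Section 6 allows full-dose continuation in cases where the tables call for suspension, which is a safety matter. Section 6 also calls for a reduction in cases where Table 7-1 says none is required. Because Section 6 does not allow dose escalation, such a reduction would ordinarily last for the rest of treatment. Imaging falls in the week before each odd cycle (Table 9-1), so the only scheduled on-treatment scan in the 8 (+/-4) week primary window comes just before day 57. Dosing in the first two cycles is what precedes that scan.

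**Working it through.** **The plan's own figure.** The only calculated figure in the plan is the error rates of the two-stage design (Section 12.6.2): stop if there are 0 responses in 9 patients, otherwise continue to 17 and declare success at 3 or more. The probability of success is the sum over x = 1 to 9 of C(9,x) p^x (1-p)^(9-x) × P(Bin(8,p) ≥ 3 - x).
- p = 0.05: 0.2985 × 0.0572 + 0.0629 × 0.3366 + 0.0084 = 0.0466. The plan says 0.05.
- p = 0.30: 0.1557 × 0.7447 + 0.2668 × 0.9424 + 0.5372 = 0.9045. The plan says 0.9.

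Both reproduce. Neither uses the dose-modification rules, so this point does not change them.

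**Diarrhea, side by side.** The patient starts at 200 mg twice daily, the event is treatment-related Grade 2, and one reduction means 150 mg twice daily.

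| Tolerability | Course of the diarrhea | Section 6 | Table 7-1 | Same? |
|---|---|---|---|---|
| Tolerable | resolves within 24 h | may continue at 200 | no hold, 200 | yes |
| Tolerable | first episode over 24 h | may continue at 200 | hold; reduction not required | no |
| Tolerable | persists or recurs | may continue at 200 | hold, then 150 | no |
| Intolerable | resolves within 24 h | hold, then 150 | no hold, 200 | no |
| Intolerable | first episode over 24 h | hold, then 150 | hold; reduction not required | no |
| Intolerable | persists or recurs | hold, then 150 | hold, then 150 | yes |

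Four of six combinations differ. For a first episode lasting over 24 hours, Table 7-1 differs from both branches of Section 6. Three courses are then open: continue at 200, hold and resume 200, or hold and resume 150.

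**Other nonhematologic events (Table 7-6).**

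| Tolerability | Course | Section 6 | Table 7-6 | Same? |
|---|---|---|---|---|
| Tolerable | not persistent or recurrent | may continue | no modification required | yes |
| Tolerable | persistent or recurrent | may continue | hold, then reduce | no |
| Intolerable | not persistent or recurrent | hold, then reduce | no modification required | no |
| Intolerable | persistent or recurrent | hold, then reduce | hold, then reduce | yes |

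Two of four differ.

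**Precedence.** Section 6 excepts only pneumonitis from its Grade 2 bullets, so on its face it covers diarrhea. Table 7-1 is offered as additional information, and Table 7-6 carries no priority wording. By contrast, the lead-in to Table 7-5 makes that table mandatory for hematologic toxicity, and the lead-in to Table 7-3 says it is to be followed for hepatic monitoring.

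**Illustration of exposure (assumed timings).** The planned amount to day 56 is 56 × 400 = 22,400 mg. Assume a first Grade 2 episode lasting over 24 hours, with a 3-day hold from day 8.
- Section 6, judged tolerable: 22,400 mg, 100%.
- Table 7-1, same dose resumed: 53 × 400 = 21,200 mg, 94.6%.
- Section 6, judged intolerable: 7 × 400 + 46 × 300 = 16,600 mg, 74.1%.

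With the hold starting between day 8 and day 29 and lasting 2 to 7 days, hold-and-resume gives 49/56 = 87.5% to 54/56 = 96.4%. Hold-and-reduce gives from (7 × 400 + 42 × 300)/22,400 = 68.8% to (28 × 400 + 26 × 300)/22,400 = 84.8%.

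**The case against.** The strongest reply is that much of the wording is permissive. Section 6 says a patient with tolerable Grade 2 toxicity *may* continue, so suspending under a table does not breach it. Table 7-1 says a reduction is not required, which does not forbid one. In each differing row above, a site that took the more restrictive action could claim to satisfy both texts. This softens the conflict but does not remove it. Nothing tells a site to take the more restrictive of the two. One text allows dosing to go on where the other suspends it, and one calls for a reduction the other does not require. The second diarrhea row also assumes that the first hold ended in a return to the same dose.

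A second reply is that Section 6 is headed as general guidance, so the specific tables should control. That is a natural reading but is never stated for Tables 7-1 and 7-6, although the protocol does use binding words for Tables 7-3 and 7-5. Section 7.2, which opens the part containing the tables, itself refers to intolerable reactions. Tolerability is thus not foreign to Section 7, but Section 7.2 does not settle which text governs.

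A reader might also extend the point to ALT/AST, where Table 7-3 has a row for "Persistent or Recurrent Grade 2, or Grade 3", or to hematologic toxicity. The binding lead-ins to Tables 7-3 and 7-5 do not support that, and both tables are left out here.

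On consequences, the reply is largely right. The comparison of 100% with 74.1% sets a tolerable case against an intolerable one, for which some difference is expected. Dose changes are recorded, and compliance and duration of exposure are summarized (Sections 6 and 12.3).

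**Conclusion.** The inconsistency is real for Grade 2 diarrhea (4 of 6 combinations) and for other nonhematologic Grade 2 events (2 of 4). It is a contradiction between stated rules, not a missing detail, and it matters for safety and for uniform dosing across sites.

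A reader might go further and infer three different doses for one patient, or that the tables in general hold without reducing. The documents support neither. There are three courses over two dose levels. Once tolerability and duration are fixed, a patient faces at most two differing instructions, so all three courses are open only because investigators may judge *tolerable* differently. A hold for which no reduction is required appears in one Grade 2 row only, that for diarrhea unresolved at 24 hours.

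Nor do the documents show an effect on the primary result. Type I error (0.0466) and power (0.9045) are untouched, and nothing links a one-level reduction to response. The exposure percentages rest on assumed onset and hold length. The documents give no Grade 2 diarrhea rate, so the number of patients affected cannot be computed.

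**What to change.** Reconcile the first two bullets of Section 6 with the Grade 2 rows of Tables 7-1 and 7-6. Add one sentence stating which governs when they differ, so that each Grade 2 event leads to one action: continue, hold, or hold and reduce. If tolerability stays as a criterion, define it. Which rule is kept is for the clinical team to decide; none is proposed here. The cost is a short protocol amendment and a site memo, with no added procedures, patients or analyses.

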7.3.3 General Guidance for Interstitial lung disease (ILD)/Pneumonitis events

Interstitial lung disease (ILD) /pneumonitis has been identified as an adverse drug reaction for abemaciclib. The majority of events observed in clinical trials were Grade 1 or Grade 2 with serious cases and fatal events reported. Additional information is available in the IB. Monitor for clinical symptoms or radiological changes indicative of ILD/pneumonitis and ask your patients to report any new or worsening pulmonary symptoms such as dyspnea, cough, and fever, and investigate and treat as per your local clinical practice (including corticosteroids as appropriate). If ILD/pneumonitis is suspected, investigations may include imaging, such as high resolution computed tomography, bronchoalveolar lavage, and biopsy as clinically indicated. Discontinue abemaciclib in cases of severe (Grade 3 or 4) ILD/pneumonitis (see also Table 7-2: *refer to dose adjustment table for interstitial lung*

disease/pneumonitis).

Table 7-2: Dose Modification and Management — Interstitial Lung Disease/Pneumonitis

CTCAE Grade	Abemaciclib Dose Modifications
Grade 1 or 2	No dose modification is required.
Persistent or recurrent Grade 2 toxicity that does not resolve with maximal supportive measures within 7 days to baseline or Grade 1	Suspend dose until toxicity resolves to baseline or Grade 1. Resume at next lower dose.
Grade 3 or 4	Discontinue abemaciclib.

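### Section 6 permits restart after non-life-threatening Grade 3 or 4 pneumonitis, 7.3.3 and Table 7-2 order discontinuation, and nothing says which prevails

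*Combined protocol and SAP*

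**What the plan says.** Section 6 gives three graded rules under its general guidelines for dose modification.

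- Grade 1 and tolerable Grade 2: "For grade 1 and tolerable grade 2 treatment-related toxicities, with the exception of pneumonitis, patients may continue at the current dose of abemaciclib".
- Intolerable Grade 2: "For intolerable grade 2 treatment-related toxicities, with the exception of pneumonitis, dosing should be interrupted until resolution to grade 1 or lower", and then the dose is reduced.
- Grade 3 or 4: "For grade 3 or grade 4 treatment-related toxicity, that is not considered by the investigator to be life-threatening, dosing should be interrupted". The interruption lasts until Grade 1 or lower. The rule then continues: "Following recovery from grade 3 or grade 4 events, study treatment may continue following a dose reduction to the next dose level", on condition that the investigator judges the patient still to be benefiting. Permanent discontinuation is required only for events judged life-threatening.

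The first two rules except pneumonitis by name. The third does not.

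Section 7.3.3 says: "Discontinue abemaciclib in cases of severe (Grade 3 or 4) ILD/pneumonitis". The Grade 3 or 4 row of Table 7-2 repeats this. Neither makes it depend on whether the event was life-threatening, and neither offers a restart.

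Section 6 points to Section 7.3.1 for dose levels and does not refer to 7.3.3 or Table 7-2. Neither section says which text governs when they differ.

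**The concern.** An exception that is stated twice and then left out can be read as leaving pneumonitis inside the Grade 3 or 4 rule. On that reading Section 6 permits what 7.3.3 forbids, for the same event in the same patient.

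The event matters. Section 7.3.3 identifies ILD/pneumonitis as an adverse reaction to abemaciclib and adds: "The majority of events observed in clinical trials were Grade 1 or Grade 2 with serious cases and fatal events reported". The protocol provides for participating sub-sites, so two sites could handle the same event differently and each cite the protocol. A restart would also be awkward to classify as a deviation, because the site could point to Section 6 and a monitor to 7.3.3.

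**Working it through.** The plan gives no figure to reproduce. The check sets the texts side by side.

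**1. The case in dispute.** All of the following must hold: Grade 3 or 4 pneumonitis; treatment-related; judged not life-threatening; recovered to Grade 1 or lower; interruption no longer than the 56 days Section 6 allows; continued benefit in the investigator's opinion. Outside this case the texts do not collide. An event judged life-threatening, for example, is discontinued under both.

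**2. The two instructions for that case.** Section 6: treatment may resume one dose level lower. Section 7.3.3 and Table 7-2: discontinue. The first is a permission and the second an order. An investigator who stops the drug satisfies both texts. One who restarts satisfies only Section 6.

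**3. Dose at stake.** Table 4-1 sets the start at 200 mg twice daily, and 7.3.1 sets the reduction step at 50 mg. For a patient on the starting dose:

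- Section 6: 200 − 50 = 150 mg twice daily, or 300 mg/day; 300/400 = 75% of the starting daily dose.
- Table 7-2: 0 mg/day.

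**4. Evidence of intent.** The heading of 7.3.6 and the title of Table 7-6 exclude ILD/pneumonitis, so the rule there that resumes treatment at a lower dose after Grade 3 or 4 toxicity does not reach it. Exclusion criterion 4 names interstitial lung disease as an example of a condition that would preclude participation. Section 6 itself takes even Grade 1 and 2 pneumonitis out of its general rules. All three point to discontinuation, with the exception omitted from the third rule by oversight.

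**5. Is pneumonitis the only mismatch?** No. The table compares Section 6 (for toxicity that is treatment-related and judged not life-threatening) with the specific instructions.

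| Toxicity | Section 6 | Specific instruction |
|---|---|---|
| Grade 3 or 4 ILD/pneumonitis | Hold to Grade 1 or lower, may resume reduced | Table 7-2: discontinue |
| Grade 4 ALT/AST | Same | Table 7-3: discontinue |
| First Grade 3 hematologic | Same | Table 7-5: hold to Grade 2 or lower, no reduction required |
| Grade 3 or 4 venous thromboembolism | Same | VTE table: hold, resume when clinically stable, no reduction stated |

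The mismatches run both ways. The specific text is stricter for pneumonitis and Grade 4 ALT/AST, and more lenient for the other two. A site therefore cannot recover the intended scheme by always taking the stricter text. It needs a stated order of precedence.

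**The case against.** The strongest reply is that the specific instruction governs the general one. Section 6 is headed as general guidance and its restart is only permissive, whereas 7.3.3 is an unqualified order for the named event, given in the text and again in Table 7-2. The comparison above helps this reply: Section 7.3 works as a whole only if Section 6 is the default and the toxicity tables override it. For two tables the protocol nearly says so. On the liver: "The following information in Table 7-3 is to be followed for hepatic monitoring". On hematology: "The following instructions from Table 7-5 must be used to manage hematologic toxicities". There is also oversight. Under Section 7.4, sub-sites report serious events of Grade 3 or above to the overall principal investigator in writing within 24 hours, and the DSMC reviews serious events, so a serious case would normally be known centrally before recovery allowed a restart.

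Most of this stands, and it makes rechallenge unlikely. It does not remove the conflict. The precedence is inferred and not written, and Section 6 does address pneumonitis by name, so it cannot simply be read as silent on it.

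Two stronger readings are tempting, and the documents support neither. A reader might infer that a site could restart with the protocol fully behind it and without overlooking anything. That is not so, because a restart disregards an explicit order given twice. A reader might also infer that Table 7-2 is merely advisory, because 7.3.3 refers to it in passing and lacks the wording used for Tables 7-3 and 7-5. That reference is a parenthesis on a sentence that is itself an order, and the sentence binds without the table.

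**Conclusion.** The inconsistency is in the current text and should be corrected. Section 6 permits re-exposure after severe, non-life-threatening, recovered pneumonitis; 7.3.3 and Table 7-2 forbid it; nothing written settles which prevails. Discontinuation is very probably the intended rule. What remains is textual cover for rechallenge with a drug for which fatal events of this kind are reported.

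The size is 150 mg twice daily against none per affected patient, assuming the event occurs at the starting dose. How often this would arise among 17 patients cannot be stated. The documents give no rate of Grade 3 or 4 pneumonitis, and the disputed case is narrower than any such event. A reader might also infer some effect on the trial's efficacy conclusion; nothing in the documents supports one, and none is claimed.

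**What to change.** Two changes to Section 6:

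1. In the third rule, after the reference to Grade 3 or 4 treatment-related toxicity, insert: *with the exception of ILD/pneumonitis (Grade 3 or 4: permanently discontinue, see 7.3.3 and Table 7-2)*.
2. Add: *Where Section 7.3 gives toxicity-specific instructions, those instructions take precedence over these general guidelines.*

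The second sentence is needed as well as the first. An exception for pneumonitis alone would leave the ALT/AST, hematologic and thromboembolism mismatches in place, and could suggest that Section 6 governs them.

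If the sponsor-investigator does want rechallenge after Grade 3 pneumonitis, 7.3.3 and Table 7-2 must be changed and justified instead.

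The cost is a wording amendment, an IRB modification and a memo to sites, with no added visits, tests or patients. The downside is that an investigator loses the Section 6 option to restart a patient who is benefiting after non-life-threatening Grade 3 or 4 pneumonitis, in a disease with few alternatives. Section 7.3.3 and Table 7-2 already deny that option.
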